Encouraging Overdue Healthcare Appointment Scheduling
Among Patients with Chronic Diseases

Statistical Analysis Plan

August 2, 2021

Statistical Analysis Plan

Brief Summary

The goal of this study is to determine the most effective messages for encouraging patients with chronic conditions, who have not seen their doctor in at least one year, to return to the clinic. Study participants will receive postcards or letters encouraging them to make an appointment. Researchers will assess whether messages increase appointment scheduling (and attendance).

Study Populations

This study includes four distinct populations: 1. **Medicaid** patients (pending approval of study materials for this population), 2. Geisinger Health Plan (GHP) members who are also Geisinger patients (**patient-members**), 3. GHP **members** only, and 4. Geisinger **patients** only.

It is important to note these distinct populations because appointment scheduling data (our primary outcome) are available only for patients and patient-members. Patient and patient-member data will be analyzed together in this study. Data for members and Medicaid patients (if available) will be included as separate subsamples in the study.

Project Status

The study design is finalized, and mailers were sent to patients, patient-members, and members, but data have not yet been extracted or analyzed as of the time this document was uploaded.

A sample of Medicaid patients may also be included, pending approval of study materials for this population.

Power Analysis

At baseline, an estimated 10% of patients may schedule appointments. The study will achieve 80% power to observe about a 3.1% absolute increase (or a 31% relative increase) in scheduled appointments in any of the intervention arms, relative to the control arm, at a two-tailed $p < .05$ with $n = 1,643$ patients per arm. A primary outcome analysis compares data from the control arm to combined experimental arms. Therefore, the sample described below will allow power to detect an even smaller effect for this analysis.

Estimated Sample Sizes

Geisinger patients/patient-members, GHP members, and Medicaid patients (if approved) will be randomly assigned to 1 of 4 arms. Estimated enrollment for each subsample and arm is listed below, with intervention arms highlighted in blue:

Arm	Patients/ Patient-members	Members	Medicaid
1. Standard Outreach Postcard	1,643	2,163	~794
2. Humorous Postcard	1,643	2,163	~794
3. Physician Letter	1,643	2,163	~795
4. Control	1,643	2,163	~795
Total	6,572	8,652	3,182

Study Timeline

Mailers were sent to patients, patient-members, and members in late July, 2021 across 3 drop dates. Mailers from each arm were evenly divided, at random, across the dates.

If materials for Medicaid patients are approved, this subsample will receive modified versions of the mailers in late 2021 (drop dates TBD), and data will be included in analyses of secondary outcomes.

Planned Analyses

Analyses will test whether participants in any of the study arms are more likely to schedule or attend appointments relative to those in a no-contact control arm.

Primary analyses will test whether Geisinger patients or patient-members who receive mailers are more likely to schedule an appointment relative to those in the no-contact control arm.

Secondary analyses will assess the following:

- Whether patients or patient-members who receive mailers are more likely to attend an appointment that they scheduled during the study period, relative to control
- The relative efficacy of different mailers in increasing appointment scheduling
- The relative efficacy of different mailers in increasing appointment attendance
- Whether appointments occur sooner in mailer groups relative to control

Analyses will include a series of generalized linear models (GLMs) specifying a binary outcome and log-link function for scheduling and attendance, and a negative binomial distribution and log-link function—or another distribution and link function if better suited to the data—for appointment timing. All analyses will be run in R.

Planned outcomes and comparisons of interest are detailed below.

Notes about timeframes and analysis

Mailers were sent on 3 different drop dates. Timeframes listed below refer to the amount of time elapsed from the drop date for a given participant. For instance, the primary outcome timeframe is 30 days; thus, for the purposes of this study, a patient will be counted as having scheduled an appointment if there was an appointment scheduled in the 30 days following that patient's drop date.

Control participants will be separated into 3 drop date groups, each assigned to one of the three drop-date groups for the experimental arms. Each control group will be monitored for appointments during a date range that is aligned with that for its corresponding experimental group.

Outcomes

Primary outcome:

1. Patients – Appointment scheduling – 30 days – confirmatory
 - a. individual mailers vs. control
 - b. mailers combined vs. control

Secondary outcomes:

1. Patients – Appointment scheduling – 30 days – exploratory
 - a. outreach vs. humorous vs. letter
2. Patients – Attendance at appointments scheduled within 30 days of mailers – 180 days – exploratory
 - a. individual mailers vs. control

- b. mailers combined vs. control
- 3. Patients, Members, & Medicaid – Attendance at any appointment – 30 days – exploratory
 - a. individual mailers vs. control
 - b. mailers combined vs. control
 - c. outreach vs. humorous vs. letter
- 4. Patients, Members, & Medicaid – Attendance at any appointment – 90 days – exploratory
 - a. individual mailers vs. control
 - b. mailers combined vs. control
 - c. outreach vs. humorous vs. letter
- 5. Patients, Members, & Medicaid – Attendance at any appointment – 180 days – exploratory
 - a. individual mailers vs. control
 - b. mailers combined vs. control
 - c. outreach vs. humorous vs. letter
- 6. Patients, Members, & Medicaid – Timing of appointment – 30 days – exploratory
 - a. individual mailers vs. control
 - b. mailers combined vs. control
 - c. outreach vs. humorous vs. letter
- 7. Patients, Members, & Medicaid – Timing of appointment – 90 days – exploratory
 - a. individual mailers vs. control
 - b. mailers combined vs. control
 - c. outreach vs. humorous vs. letter
- 8. Patients, Members, & Medicaid – Timing of appointment – 180 days – exploratory
 - a. individual mailers vs. control
 - b. mailers combined vs. control
 - c. outreach vs. humorous vs. letter

Additional outcomes:

- 1. Patients – appointment scheduling within 14 days of mailers being sent – exploratory*
 - a. outreach vs. humorous vs. letter
- 2. Patients – Calls to appointment scheduling – 30 days – exploratory
 - a. individual mailers vs. control
 - b. mailers combined vs. control
 - c. outreach vs. humorous vs. letter

*Note: this analysis will inform internal operations but will not be reported in publication.

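### Does the goal of finding the best messages need a confirmatory comparison between mailers, when the SAP confirms only against control?

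*SAP*

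**What the plan says.** The Brief Summary contains two questions. The first is the goal: "The goal of this study is to determine the most effective messages for encouraging patients with chronic conditions". The second closes the same paragraph: "Researchers will assess whether messages increase appointment scheduling (and attendance"). The first compares messages with each other; the second compares messages with no message.

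The rest of the SAP treats the two differently:

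- **Power Analysis.** The 80% power is for a difference "in scheduled appointments in any of the intervention arms, relative to the control arm". The section adds that the combined comparison can detect a smaller effect.
- **Planned Analyses, primary.** "Primary analyses will test whether Geisinger patients or patient-members who receive mailers are more likely to schedule an appointment", with the no-contact arm as comparator.
- **Planned Analyses, secondary.** "The relative efficacy of different mailers in increasing appointment scheduling" is a separate item, and attendance has a matching one.
- **Outcomes.** Primary outcome 1 is confirmatory and holds "a. individual mailers vs. control" and the combined comparison. Secondary outcome 1, on the same 30-day scheduling endpoint, is "a. outreach vs. humorous vs. letter" and is labelled exploratory. The three-way comparison recurs as line c of Secondary outcomes 3 to 8 and under Additional outcomes.

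The SAP gives no detectable difference between mailers and no criterion for calling one of them the most effective.

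**The concern.** Read literally, the goal asks for a ranking, and by the SAP's own labels no confirmatory result can supply one. What the confirmatory tier does supply is three separate results, one per mailer. If one mailer is significant against control and another is not, it is tempting to report the first as better. That inference is unsound, because a difference in significance is not a significant difference.

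If someone did report the trial that way, equally good mailers would often be presented as unequal, and a health system might adopt one message over another on no evidence. The SAP contains no sentence warning against this. The direct comparison, which is the proper basis for a ranking, is exploratory and was not the basis for the sample size.

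**Working it through.** **Inputs from the SAP (Power Analysis, Estimated Sample Sizes).** Control rate 10% ("At baseline, an estimated 10% of patients may schedule appointments"), absolute increase 3.1 points and so a mailer rate of 13.1%, n = 1,643 per arm, two-sided 0.05, and one control arm shared by three mailers. The SAP states no multiplicity adjustment. Other rates below are assumptions. Everything concerns 30-day scheduling, because the SAP gives no attendance rates.

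**Step 1: reproduce the SAP's power.** The pooled proportion is (0.100 + 0.131)/2 = 0.1155.

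- SE under the null: √(2 × 0.1155 × 0.8845 / 1643) = 0.01115
- SE under the alternative: √((0.100 × 0.900 + 0.131 × 0.869) / 1643) = 0.01114
- Power: Φ((0.031 − 1.96 × 0.01115) / 0.01114) = Φ(0.82) = 79.4%

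The stated 80% is confirmed. The increase detectable at exactly 80% is 3.12 points.

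**Step 2: how often do the three results disagree when the mailers are equal?** If the tests were independent, all three would succeed in 0.794³ = 50% of trials. The shared control arm makes them positively correlated, so this was simulated: 1,000,000 four-arm trials, pooled z test, counted when significant in the mailer's favour.

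| Mailers significant against control (all at 13.1%) | Share of trials |
|---|---|
| 3 | 60% |
| 2 | 23% |
| 1 | 11% |
| 0 | 5% |

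One or two of three: 23.2% + 11.4% = 34.6%. A log-link Wald test, closer to the planned model, gives 34.8%. In 26.5% of all trials the results disagree although no two mailers differ at p < .05.

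The figure depends heavily on the assumed common rate:

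| Common mailer rate (assumed except 13.1%) | Results disagree |
|---|---|
| 11% | 28% |
| 12% | 50% |
| 12.5% | 47% |
| 13.1% | 35% |
| 14% | 13% |
| 15% | 2% |

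**Step 3: what kind of number is the 35%?** In this scenario every mailer truly beats control. Each significant result is therefore correct, and each non-significant one is a miss at the declared power. No false positive is involved. Disagreement also says little about whether a leader exists: with two mailers at 13.1% and a third 2, 3 or 3.9 points higher, the results disagree in about 32% of trials.

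**Step 4: what can the planned direct comparison show?** For a single pair starting from 13.1%, unadjusted, power is 13% for a 1-point difference, 38% for 2 points and 71% for 3.1 points. It reaches 80% at 3.5 points.

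As an illustration, suppose a mailer is called best only if it exceeds both others at p < .05, unadjusted. This rule is not in the SAP. With two rivals at 13.1%:

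| True lead | Best mailer named |
|---|---|
| 0 (all equal; any mailer named, falsely) | 1.3% |
| 2 points | 22% |
| 3 points | 54% |
| 3.9 points | 80% |

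The 3.9 points holds only for two rivals tied at 13.1%. With the runner-up at 13.1% and the third mailer at 10%, about 3.5 points is enough. A leader can be named at true leads below the 3.1 points used for sizing, though with less than 80% power.

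**Step 5: set the sections side by side.** The question about the effect of messages maps to Primary 1a and 1b. The question about which message works best maps to Secondary 1a and the later c lines. Both are planned, and each has its own line.

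**The case for a change.** The strongest case for a change is that the sentence the SAP itself calls the goal is the one its confirmatory tier does not answer. The silence matters because the confirmatory tier yields per-mailer results that look like an answer, and at the planning rates they would disagree by chance in about a third of trials with equal mailers. The SAP reports that data had not been extracted when it was uploaded, so a sentence tying any claim of a best message to Secondary 1a would cost almost nothing. The conflict also lies within this one document, so it cannot simply be left to a protocol.

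Part of this stands. The goal sentence is broader than the confirmatory tier, and a single sentence of caution would be harmless. The rest does not carry. The goal sentence uses the plural, and its own paragraph also states the question against control, so it need not mean that one winner will be declared. The SAP separates relative efficacy from the comparison with control in both Planned Analyses and Outcomes, so an analyst who follows it will rank mailers, if at all, from the direct comparison. The misreading requires an author to set that planned line aside. Detectable differences and criteria for naming a winner are optional for lines labelled exploratory.

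**Conclusion.** No change is needed. The SAP's summary sentence is looser than its tiers, but the tiers are coherent: effect against control is confirmatory and powered, and comparison between messages is planned and labelled exploratory. That label fits, since a 2-point difference between two mailers would be detected in only 38% of trials, and a 2-point leader would be shown to exceed both rivals in only 22%.

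The 35% disagreement rate is correct at 10% and 13.1% with unadjusted tests, but it describes ordinary loss of power across three valid tests. It would do harm only if results against control were read as a ranking, which the SAP does not propose. Its size rests on all three mailers sharing one rate, and it runs from 2% to 50% as that rate varies between 11% and 15%. The sensible reading, that any statement about the best message rests on the direct comparison and is exploratory, already follows from the Outcomes section.

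### Do secondary outcomes 3–8 pool three populations that the SAP calls separate, in models that ignore subsample and drop date?

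*SAP*

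**What the plan says.** - **Study Populations** gives two adjacent rules. For patients and patient-members: "Patient and patient-member data will be analyzed together in this study". For the other two groups: "Data for members and Medicaid patients (if available) will be included as separate subsamples in the study".
- **Outcomes** heads secondary outcomes 3–8 with all three populations at once, for example "Patients, Members, & Medicaid – Attendance at any appointment – 30 days – exploratory". All six are marked exploratory.
- **Planned Analyses** gives the form of the models: "Analyses will include a series of generalized linear models (GLMs) specifying a binary outcome and log-link function for scheduling and attendance". For timing it names a negative binomial model with log link, "or another distribution and link function if better suited to the data". No predictors of any kind are listed.
- **Study Timeline** says of the Medicaid group, whose inclusion depends on approval: "this subsample will receive modified versions of the mailers in late 2021 (drop dates TBD), and data will be included in analyses of secondary outcomes". The other groups were mailed in late July 2021 on three dates: "Mailers from each arm were evenly divided, at random, across the dates".
- **Notes about timeframes and analysis** starts each person's follow-up at his or her own drop date and splits controls into three groups with matching date windows.

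**The concern.** Taken alone, the outcome list seems to define one analysis over three populations, and the Study Timeline seems to add Medicaid to it. If that is the plan, three things look wrong.

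1. The arm labels would not mean the same intervention throughout, because Medicaid would get modified mailers months after the others.
2. The quantity estimated would depend on an approval still pending. An effect confined to one population would also be diluted.
3. A model without subsample or drop date would leave out factors that structure the design, with some loss of precision.

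If the choice between pooled and separate analysis is open, it could also be made after results are seen. Thirty-day and 90-day follow-up from late July ends in late August and late October 2021, possibly before the Medicaid mailing. Six of the eight secondary outcomes are affected.

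**Working it through.** **1. The SAP's own figure.** The only power statement concerns scheduling in patients: 10% vs 13.1%, 1,643 per arm, two-sided 0.05.

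- Mean rate 0.1155. SE under the null = √(2 × 0.1155 × 0.8845 / 1,643) = 0.01115.
- SE under the alternative = √((0.10 × 0.90 + 0.131 × 0.869) / 1,643) = 0.01114.
- z = (0.031 − 1.96 × 0.01115) / 0.01114 ≈ 0.82, so power is 79.4% against the stated 80%.

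It reproduces, but it does not concern outcomes 3–8.

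**2. Is pooling stated?** Study Populations merges patients with patient-members and, in the next sentence, keeps members and Medicaid apart. The outcome list says combined where arms are merged, but uses no such word for populations. Scheduling data exist only for patients and patient-members, so the list needs a label showing which outcomes are available in which groups. The shared label does that. A series of GLMs also fits separate models. Adding Medicaid data to the secondary analyses is compatible with either reading.

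**3. If someone pooled anyway, would omitting the subsample bias the arm effect?** Inputs from Estimated Sample Sizes:

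| | Patients | Members | Medicaid |
|---|---|---|---|
| Control | 1,643 | 2,163 | ~795 |
| Total | 6,572 | 8,652 | 3,182 |
| Control share | 25.0% | 25.0% | 25.0% |
| Share of 18,406 | 35.7% | 47.0% | 17.3% |

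The control share is the same in each group, so subsample is not associated with arm. The SAP gives no attendance rates, so the control rates below are assumptions, as is the risk ratio (RR) of 1.31, borrowed from the scheduling power statement. The comparison is all mailers (4,929 + 6,489 + 2,383 = 13,801) against control (1,643 + 2,163 + 795 = 4,601).

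Worked case, control rates 5/25/40% and common RR 1.31:

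- Control: (82.15 + 540.75 + 318) / 4,601 = 0.2045.
- Mailers: 1.31 × (246.45 + 1,622.25 + 953.2) / 13,801 = 0.2679.
- Crude RR = 1.3098; Mantel-Haenszel RR = 1.3100.
- Crude SE of the risk difference = √(0.2045 × 0.7955 / 4,601 + 0.2679 × 0.7321 / 13,801) = 0.00704.
- Stratified SE, the square root of Σ (subsample share)² × (within-subsample variance of the difference), = 0.00664. Ratio 1.061.

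| Assumed control rates (patients/members/Medicaid) | Crude RR | Stratified RR | Crude SE / stratified SE |
|---|---|---|---|
| 10/10/10% | 1.3100 | 1.3100 | 1.000 |
| 10/20/5% | 1.3101 | 1.3100 | 1.018 |
| 10/30/3% | 1.3102 | 1.3100 | 1.053 |
| 5/25/40% | 1.3098 | 1.3100 | 1.061 |

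With no effect anywhere, the crude RR lies between 0.9999 and 1.0001.

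These sums cover attendance (outcomes 3–5). For timing, the same balance holds if everyone randomised contributes. If only attenders contribute, the population mix could differ by arm when effects differ. That was not calculated, and analysis within each subsample avoids it.

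**4. What would pooling change if effects differ?**

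- RR 1.31 in patients only, equal baselines: 0.357 × 1.31 + 0.643 × 1.00 = 1.11.
- RR 1.31 in patients and members, 1.00 in Medicaid, equal baselines: 0.827 × 1.31 + 0.173 × 1.00 = 1.26. Over the four sets of control rates above, the result runs from 1.21 to 1.30.

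These are averages over populations. They describe a pooled analysis, not one by subsample.

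**5. Drop date and season.** Each mailer arm was spread evenly and at random over the dates, and controls are observed in matching windows. The three dates already used all fall in late July. The seasonal difference applies only to Medicaid, which has its own control arm, so season does not confound its comparison.

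**The case for a change.** The strongest case is that the SAP never says in one sentence whether outcomes 3–8 are run by subsample or pooled, and that two analysts could therefore report different results. The cost under pooling could be large. With a 10% baseline everywhere and RR 1.31 in patients only, power for one mailer against control would fall from about 79% (1,643 per arm) to about 41% (about 4,601 per arm). Early results might be in hand before the Medicaid mailing, so the choice could be informed by data. A line of text costs almost nothing, since the SAP reports that no data had been extracted.

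Much of this is fair as description. The rule is implied and not spelled out, and pooling the modified Medicaid mailers with the rest would change what is estimated. But the loss arises only if analysts set aside the sentence that keeps members and Medicaid apart. The proposed remedy, reporting each subsample on its own, is what that sentence already says. Subsample and interaction terms would be needed only for a pooled analysis that the SAP does not announce. Silence about model terms is not a statement that there are none. A drop-date term across three late-July dates has no demonstrated gain.

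**Conclusion.** No change follows. This is a gap in detail that analysts can fill from the SAP itself: patients with patient-members, members, and Medicaid are analysed as three groups, each against its own randomised controls. Followed that way, the different Medicaid mailers and season are never mixed with the rest.

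If a pooled model were fitted without a subsample term, the arm contrast for attendance would still be unbiased for the population average. Crude and stratified ratios agree to within 0.0002 under a common effect, and the standard error errs on the cautious side by 0% to about 6%. This rests on the SAP's equal allocation within each subsample and on assumed attendance rates, since the SAP gives none. The dilution figures (1.11, and 1.21 to 1.30, against 1.31) also need an assumed absence of effect in some populations.

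The stakes are limited. Outcomes 3–8 are exploratory, Medicaid inclusion is conditional, and the confirmatory scheduling outcome is confined to patients and patient-members.

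### Does the Medicaid column of the sample-size table need correcting because its arms sum to 3,178 and not 3,182?

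*SAP*

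**What the plan says.** Under Estimated Sample Sizes, the SAP says that each subsample "will be randomly assigned to 1 of 4 arms". It introduces the table with "Estimated enrollment for each subsample and arm is listed below". The four rows, with columns in the order patients/patient-members, members, Medicaid, are:

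- "1. Standard Outreach Postcard 1,643 2,163 ~794"
- "2. Humorous Postcard 1,643 2,163 ~794"
- "3. Physician Letter 1,643 2,163 ~795"
- "4. Control 1,643 2,163 ~795"

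The closing row is "Total 6,572 8,652 3,182". Every Medicaid arm figure carries a tilde. The Medicaid total does not, and neither does any figure in the other two columns.

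The sections Study Populations, Project Status and Study Timeline all make the Medicaid subsample conditional on approval of its materials, with mailing dates not yet set. If it is included, Study Timeline says its "data will be included in analyses of secondary outcomes".

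**The concern.** A column total should equal the sum of its parts, and this one does not. The other two columns do, so the last row is evidently meant as a plain sum and only the Medicaid entry fails. The Medicaid arm figures also look as if they were derived from a different total from the one printed, which suggests that one of them was not updated.

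This table is the only place where the SAP gives the Medicaid sample size and its split across arms. When the SAP was written, mailers to the other subsamples had gone out, while the Medicaid mailing was still ahead. A reader who later compared the enrolled numbers with the plan would find two planned figures. That reader could not tell from the SAP whether a difference of four was a typing slip or people lost between listing and allocation.

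**Working it through.** **Inputs.** All come from the Estimated Sample Sizes table: 1,643 in each patient/patient-member arm, 2,163 in each member arm, and about 794, 794, 795 and 795 in the Medicaid arms. The stated totals are 6,572, 8,652 and 3,182.

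**Step 1: reproduce the totals.**

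| Column | Sum of arms | Stated | Gap |
|---|---|---|---|
| Patients/patient-members | 4 × 1,643 = 6,572 | 6,572 | 0 |
| Members | 4 × 2,163 = 8,652 | 8,652 | 0 |
| Medicaid | 794 + 794 + 795 + 795 = 3,178 | 3,182 | 4 |

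The relative gap is 4 / 3,182 = 0.13%.

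**Step 2: can rounding explain it?** If each arm had been rounded to the nearest whole person, the unrounded values could be at most 794.5, 794.5, 795.5 and 795.5. These sum to 3,180, still 2 short of 3,182. Rounding in that sense does not close the gap.

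**Step 3: which figure is off?** An even split of 3,182 is 3,182 / 4 = 795.5 per arm, that is 795, 795, 796 and 796. An even split of 3,178 is 3,178 / 4 = 794.5, that is 794, 794, 795 and 795, exactly the arms printed. So the arms fit a total of 3,178. The SAP does not show whether the arms or the total is the intended figure.

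**Step 4: does anything depend on it?**

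- *Power statement.* Power Analysis uses n = 1,643 patients per arm, a 10% baseline and a 3.1-point increase. Recomputed for 10% against 13.1% at two-sided 0.05, power is 0.794, in line with the stated 80%. No Medicaid figure enters.
- *Primary outcome.* Study Populations says that scheduling data exist only for patients and patient-members, so Medicaid cannot contribute.
- *Secondary outcomes.* Medicaid appears in secondary outcomes 3 to 8, all labelled exploratory, and is kept as a separate subsample. No sample-size target or power claim is attached to it.
- *Precision within Medicaid.* The standard error scales with one over the square root of n. Moving from 3,182 to 3,178 multiplies it by √(3,182 / 3,178) = 1.0006, a change of 0.06%.
- *Illustrative power.* The SAP gives no Medicaid effect size. If the 10% against 13.1% contrast is borrowed purely as an assumption, power is 0.489 with 794 per arm and 0.490 with 795.5 per arm.

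**The case for a change.** The best case for amending the table is that the arithmetic is beyond dispute, the correction touches one to four cells, and this was the one column that could still be put right before allocation. Calling the figures estimates does not excuse the mismatch: an estimate may turn out wrong, but its parts should still add to its own total. Nor does the tilde fully dispose of the point, since loosely rounded arms would more naturally all read the same, whereas these follow the exact even split of 3,178.

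The finding of inconsistency stands. What does not stand is the claim of consequence. The tilde appears only on the Medicaid arms, so the authors marked this column as provisional, and an average of 795.5 per arm is not far from about 794 or 795 in ordinary usage. It goes too far to say that a figure is wrong, as opposed to saying that approximate arms do not add to the total. The SAP also gives this cell no role as a reference for randomisation or participant flow. A flow count reports the people actually enrolled, and a difference of four from an estimate for a group that might not be enrolled at all would not signal a deviation.

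**Conclusion.** The Medicaid arms sum to 3,178 against a stated 3,182. The inconsistency is genuine and neither rounding nor anything else in the SAP explains it. It amounts to 4 people, 0.13% of the subsample, or about one person per arm.

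It is a clerical slip, and correcting it would gain nothing for the analysis. The power calculation, the primary comparison and the planned models read the same under either figure. Anyone carrying out the Medicaid analyses would use the numbers actually randomised. Aligning the cells would be harmless housekeeping if the table were reissued for another reason, but it is not a change that the plan needs.

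This conclusion rests on three points in the SAP: the Medicaid arm sizes are presented as approximate and conditional on approval; Medicaid enters only the exploratory secondary outcomes, as a separate subsample; and no analysis set, target or threshold is tied to 3,182.

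### Does secondary outcome 2 compare attendance only among patients who scheduled, and so condition on the primary outcome?

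*SAP*

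**What the plan says.** The SAP describes this outcome twice. The first secondary bullet under Planned Analyses takes as its subject the patients and patient-members sent a mailer, and asks if they are "more likely to attend an appointment that they scheduled during the study period, relative to control". The Outcomes list has it as secondary outcome 2: "Patients – Attendance at appointments scheduled within 30 days of mailers – 180 days – exploratory". It is to be compared for each mailer against control and for all mailers combined against control.

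Four other statements bear on how to read it:

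- The sentence that opens the Planned Analyses section: "Analyses will test whether participants in any of the study arms are more likely to schedule or attend appointments relative to those in a no-contact" (the sentence goes on to name that arm as control).
- The primary outcome: "Patients – Appointment scheduling – 30 days – confirmatory".
- The model: "generalized linear models (GLMs) specifying a binary outcome and log-link function for scheduling and attendance". No analysis set is attached to it.
- The last of three broader attendance outcomes (secondary outcomes 3 to 5): "Patients, Members, & Medicaid – Attendance at any appointment – 180 days – exploratory". The other two are the same measure at 30 and 90 days.

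Nowhere does the SAP state in words the denominator for secondary outcome 2.

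**The concern.** Both descriptions tie attendance to an appointment already booked, so an analyst could take the outcome as a show rate: of those who scheduled, how many came. That would be a poor comparison between arms. Scheduling follows randomisation and is what the mailers are meant to change. If a mailer works, its schedulers include people who would not have booked without it, and the control arm has no matching group. If those extra patients are less committed, attendance among schedulers falls in the mailer arm even though more people reach the clinic. The comparison would also use only a small, self-selected part of each arm. The model does not settle the matter, since a log-link binary GLM runs on either data set.

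**Working it through.** **The SAP's own figure.** The Power Analysis section gives 10% scheduling in control, an increase of 3.1 points, 1,643 per arm, two-sided 0.05 and 80% power. The usual two-proportion formula is

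n = [1.960 × √(2 × p̄ × (1 − p̄)) + 0.842 × √(p₁(1 − p₁) + p₂(1 − p₂))]² / (p₂ − p₁)²

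With p₁ = 0.10, p₂ = 0.131 and p̄ = 0.1155 it gives 1,668 per arm. Power at 1,643 is 79.4%. The stated 80% is reproduced, so these scheduling rates can be used below.

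**Patients who would schedule, per arm.** Control: 1,643 × 0.10 ≈ 164. Mailer: 1,643 × 0.131 ≈ 215.

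**The two denominators.** The SAP gives no attendance rates, so these are assumptions: 80% of usual schedulers attend, and a share q of the extra 3.1% attend, with q = 60% and a range of 40% to 80%.

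- Attendance per randomised patient, mailer: 0.10 × 0.80 + 0.031 × q. Control: 0.10 × 0.80 = 8.0%.
- Attendance among schedulers, mailer: (0.10 × 0.80 + 0.031 × q) / 0.131. Control: 80.0%.

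| q | All randomised, mailer vs control | Risk ratio | Schedulers only, mailer vs control | Risk ratio |
|---|---|---|---|---|
| 40% | 9.2% vs 8.0% | 1.16 | 70.5% vs 80.0% | 0.88 |
| 60% | 9.9% vs 8.0% | 1.23 | 75.3% vs 80.0% | 0.94 |
| 80% | 10.5% vs 8.0% | 1.31 | 80.0% vs 80.0% | 1.00 |

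The two analyses can point in opposite directions, so the denominator matters.

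**Sampling error in the middle row, one mailer against control.**

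- Schedulers only: SE = √(0.753 × 0.247 / 215 + 0.80 × 0.20 / 164) ≈ 4.3 points, so z ≈ 4.7 / 4.3 ≈ 1.1.
- All randomised: SE = √(0.0986 × 0.9014 / 1,643 + 0.08 × 0.92 / 1,643) ≈ 0.99 points, so z ≈ 1.86 / 0.99 ≈ 1.9.

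Neither passes two-sided 0.05. With the three mailers combined (3 × 1,643 = 4,929 patients), the all-randomised comparison gives z ≈ 2.3. The schedulers-only analysis with 164 and 215 patients has 80% power only for a difference of about 10.2 points at 80% control attendance.

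**Which denominator the text supports.**

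1. The full bullet is about patients and patient-members who receive mailers, not those who scheduled. The primary question is built the same way, and no one would read that as a subset.
2. The opening sentence of Planned Analyses compares participants by arm, for scheduling and attendance alike.
3. Each line in the Outcomes list runs population, outcome, timeframe, status. For secondary outcome 2 the population is patients, as for the primary outcome. The scheduling window sits in the outcome field, where it says which appointment counts.
4. The one explicit counting rule, in the notes on timeframes, classifies each patient as having scheduled or not from that patient's drop date. Extended to this outcome, it gives yes for a patient who booked within 30 days and attended that appointment by day 180, and no for everyone else.
5. Outcome 2 is limited to patients for a practical reason given under Study Populations: scheduling data exist only for patients and patient-members. Its difference from outcomes 3 to 5 therefore does not imply a schedulers-only analysis.

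**The case for a change.** The best case for a change is that the wording excludes neither reading, the SAP spells out a counting rule for scheduling but not for this outcome, and a choice left open until results are known could reverse the conclusion. The SAP says data had not been extracted or analysed, so one sentence would have settled it at almost no cost. Outcomes 3 to 5 do not fully stand in, because they count any appointment and not those booked in the mailer window.

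Much of this stands. The denominator is unstated, a schedulers-only test against control would be open to real bias, and the arithmetic is correct. What does not stand is the step from an unstated denominator to a plan that conditions on scheduling. That needs the less natural reading of both descriptions. The illustration also rests on assumed attendance rates, with the extra schedulers never attending more often than the usual ones, so the bias can only run against the mailer or vanish. In the middle case, a single-mailer comparison would show neither clear harm nor clear benefit.

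**Conclusion.** No change is needed. Read naturally, secondary outcome 2 is already a yes/no outcome over all 1,643 patients and patient-members per arm: booked within 30 days of the drop date and attended that appointment within 180 days. Followed that way, it keeps the randomised comparison. The missing denominator is a gap that a competent analyst would fill in the same way.

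If it were filled the other way, the risk ratio could move from 1.23 to 0.94 in the middle case. Over the assumed range of 40% to 80% attendance among the extra schedulers, it would be 0.88 to 1.00 instead of 1.16 to 1.31. These figures take the SAP's 10% and 13.1% scheduling rates and an assumed 80% attendance among usual schedulers.

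Even then the damage would be contained. The outcome is exploratory, the confirmatory scheduling analysis is untouched, and attendance at any appointment, with no scheduling condition, is planned at three time points. A misleading show rate would not stand alone.
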